9.7. Safety Evaluations

Safety and tolerability will be evaluated throughout the study from signing of the ICF (including diagnostic ICF, if applicable) onwards until the last study-related activity (end of study/early withdrawal).

Details regarding the DRC are provided in [Section 11.9](#).

Any clinically relevant changes occurring during the study must be recorded on the AE section of the eCRF.

Any clinically significant abnormalities persisting at the end of the study/early withdrawal will be followed by the investigator until resolution or until a clinically stable endpoint is reached.

The study will include the following evaluations of safety and tolerability according to the time points provided in the [TIME AND EVENTS SCHEDULE](#):

Adverse Events

Adverse events will be reported by the subject (or, when appropriate, by a caregiver, surrogate, or the subject's legally acceptable representative) for the duration of the study. Adverse events will be followed by the investigator as specified in Section 12. Grading will be determined according to the criteria specified in the DMID adult toxicity tables (see [Attachment 1](#)).

Special attention will be paid to those subjects who discontinue the study for an AE, or who experience an AE of at least grade 3, or an SAE.

Exacerbations of underlying pulmonary disease (eg, asthma, COPD) occurring after treatment start, bacterial superinfections of presumed respiratory origin per investigator assessment, and exacerbations of underlying cardiovascular conditions should be reported as AE and are considered events of interest (complications associated with RSV per investigator assessment). Further details on these events of interest will be captured separately in the eCRF.

Evaluations of signs and symptoms of RSV disease that are part of the efficacy evaluations (with exception of the complications mentioned above) will not be reported as AEs.

Clinical Laboratory Tests

Blood samples for serum chemistry and hematology and a urine sample for urinalysis will be collected at time points indicated in the [TIME AND EVENTS SCHEDULE](#) and analyzed at the central laboratory. The investigator must review the laboratory results, document this review, and record any clinically relevant changes occurring during the study in the AE section of the eCRF. Laboratory reports must be filed with the source documents.

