In case a grade 3 or grade 4 laboratory abnormality occurs, a confirmatory test must be performed preferably within 48 hours but no later than 72 hours after the results have become available.

Any values that indicate a potential safety concern will be assessed by the investigator and appropriate follow-up actions, including potential discontinuation from treatment, will be carried out.

The following tests will be performed by the central laboratory:

- Hematology Panel
 - hemoglobin
 - hematocrit
 - RBC count
 - WBC differential:
 - * neutrophils
 - * lymphocytes

- | | |
|-------------------------------------|-----------------|
| -reticulocyte count | * monocytes |
| -RBC parameters: | * eosinophils |
| * mean corpuscular hemoglobin (MCH) | * basophils |
| * MCH concentration | -platelet count |
| * mean corpuscular volume | |
| -WBC count | |

Note: A WBC evaluation may include any abnormal cells, which will then be reported by the laboratory. An RBC evaluation may include abnormalities in the RBC count, RBC parameters, or RBC morphology, which will then be reported by the laboratory. In addition, any other abnormal cells in a blood smear will also be reported.

- Coagulation parameters: PT, aPTT and international normalized ratio
- Serum Chemistry Panel

- | | |
|-----------------------|--|
| -alkaline phosphatase | -glucose |
| -ALT | -potassium |
| -AST | -sodium |
| -bicarbonate | -total bilirubin (direct and indirect) |
| -uric acid | -urea |
| -chloride | -phosphorus |
| -magnesium | -calcium |

- Urinalysis

Dipstick

- specific gravity
- pH
- glucose
- protein
- blood
- ketones
- bilirubin
- urobilinogen
- nitrite
- leukocyte esterase

Sediment (if dipstick result is abnormal)

- RBC
- WBC
- epithelial cells
- crystals
- casts
- bacteria

Dipstick will be performed per the [TIME AND EVENTS SCHEDULE](#). If dipstick result is abnormal, flow cytometry or microscopy will be used to measure sediment. In case of discordance between the dipstick results and the flow cytometric results, the sediment will be examined microscopically.

In the microscopic examination, observations other than the presence of WBC, RBC and casts may also be reported by the laboratory.

- Renal function testing:
 - Serum creatinine and estimated Glomerular Filtration Rate (eGFR) based on creatinine by Cockcroft-Gault formula²⁵
 - Serum cystatine C and eGFR based on cystatine C²⁵

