A physical examination (including height [only at screening] and body weight measurements) and skin examination will be performed at the visits indicated in the [TIME AND EVENTS SCHEDULE](#).

A skin examination includes an examination of the mucous membranes, but does not include a vaginal or rectal examination. However, if the subject develops a cutaneous reaction/rash, vaginal and rectal examinations may be done if clinically relevant.

Any clinically relevant changes occurring during the study must be recorded in the AE Section of the eCRF.

Specific Toxicities

Rash

In case there are skin changes, a correct diagnosis has to be made by the investigator or a dermatologist, preferably within 24 hours of detection. If a diagnosis of rash is made, the investigator will discuss this with the sponsor, preferably within 24 hours of the investigator's awareness of the rash. An assessment of severity grade should be made using the criteria specified in the DMID adult toxicity tables (see [Attachment 1](#)).

If the rash is considered to be most likely due to RSV, concomitant illness or non-study medication, standard management, including discontinuation of the likely causative agent, should be undertaken.

If a causal relationship between the rash and the study drug is reasonably suspected, then the visits and assessments will be performed as indicated in [Attachment 5](#). Unscheduled follow-up visits for close follow-up of rash will be performed based on the grade (severity) of the rash. At the investigator's discretion, additional visits and assessments can be performed.

AST and ALT Evaluation

Management will be at the discretion of the investigator and should follow generally accepted medical standards.

For grade 3 or 4 laboratory abnormalities, subjects should have a confirmatory measurement, preferably within 48 hours after the laboratory results become available to the site. This management scheme is for confirmed laboratory abnormalities and not for isolated events.

Grade 1 (1.1 to <2.0 x upper limit of normal [ULN]), or Grade 2 (>2.0 to ≤3.0 x ULN)

Subjects may continue the intake of study drug.

Subjects should be followed until resolution (return to baseline) or stabilization of AST/ALT elevation (to be agreed upon with the sponsor).

Grade 3 (>3.0 to 8.0 x ULN), or Grade 4 (>8.0 x ULN)

Subjects will permanently discontinue the intake of study drug.

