9.9. Sample Collection and Handling

The actual dates and times of sample collection must be recorded in the eCRF or laboratory requisition form.

Refer to the [TIME AND EVENTS SCHEDULE](#) for the timing and frequency of all sample collections.

Instructions for the collection, handling, storage, and shipment of samples are found in the laboratory manual that will be provided. Collection, handling, storage, and shipment of samples must be under the specified, and where applicable, controlled temperature conditions as indicated in the laboratory manual.

**10. SUBJECT COMPLETION/DISCONTINUATION OF STUDY TREATMENT/
WITHDRAWAL FROM THE STUDY****10.1. Completion**

A subject will be considered to have completed the treatment period of the study if he or she has completed dosing on the 7 days of the dosing period and the Day 8 visit. A subject is considered to have completed the study if he or she has also completed assessments of the last follow-up visit.

10.2. Discontinuation of Study Treatment/Withdrawal from the Study**Discontinuation of Study Treatment**

A subject will not be automatically withdrawn from the study if he or she has to discontinue treatment before the end of the treatment regimen.

A subject's study treatment must be discontinued if:

- The subject withdraws consent.
- The investigator believes that for safety reasons or tolerability reasons (eg, AE) it is in the best interest of the subject to discontinue study treatment.
- The subject becomes pregnant.

- The subject has a confirmed QTcF interval >500 ms at the Day 3 visit, per the machine read parameter result. Confirmation needs to be obtained during the visit by repeat triplicate ECG recording.
- The subject is reported with the following laboratory abnormalities: AST or ALT increases ≥ 3 x ULN at screening, confirmed in a repeat test, to be performed within 48 hours of the result being available at the site.
- The subject is reported with any other laboratory abnormality of grade 3 or 4, except for grade 3 or 4 elevations of triglycerides, low density lipoprotein cholesterol, and/or cholesterol at screening, confirmed in a repeat test, to be performed within 48 hours of the result being available at the site.

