11.8. Safety Analyses

Safety data will be presented descriptively. No statistical testing of safety data is planned. For safety, baseline is defined as the last assessment prior to the first intake of study drug.

The population for the safety analysis will consist of all randomized subjects who received at least one dose of study drug.

Adverse Events

The verbatim terms used in the eCRF by investigators to identify AEs will be coded using the Medical Dictionary for Regulatory Activities. Treatment-emergent AEs are AEs with onset during the treatment phase or that are a consequence of a pre-existing condition that has worsened since baseline. All reported AEs will be included in the analysis. For each AE, the percentage of subjects who experience at least 1 occurrence of the given event will be summarized by treatment group.

Summaries, listings, datasets, or subject narratives may be provided, as appropriate, for those subjects who die, who discontinue treatment due to an AE, or who experience an AE of at least grade 3, or an SAE.

Clinical Laboratory Tests

Laboratory data will be summarized by type of laboratory test and by treatment. Descriptive statistics of absolute values and changes from baseline will be calculated for each laboratory analyte at baseline and at each scheduled time point.

The laboratory abnormalities will be determined according to the criteria specified in the DMID adult toxicity tables (see [Attachment 1](#)) and in accordance with the normal ranges of the clinical laboratory if no gradings are available.

Changes from baseline results will be presented in pre- versus posttreatment cross-tabulations (with classes for below, within, and above normal ranges).

Urinary renal function parameters will be analyzed for the analyte as well as for the analyte ratio over urinary creatinine.

Laboratory abnormalities will be tabulated by scheduled time point.

Electrocardiogram

The effects on cardiovascular variables will be evaluated by means of descriptive statistics and frequency tabulations.

The ECG variables that will be analyzed are heart rate, PR interval, QRS interval, QT interval, and corrected QT (QTc) interval using the following correction methods: QT corrected according to Bazett's formula, and QTcF.^{1,12,14,23}

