Attachment 1: Toxicity Tables

DIVISION OF MICROBIOLOGY AND INFECTIOUS DISEASES (DMID) ADULT TOXICITY TABLE²⁰ – NOVEMBER 2007

ABBREVIATIONS: Abbreviations utilized in the Table:

ULN = Upper Limit of Normal	LLN = Lower Limit of Normal
R _x = Therapy	Req = Required
Mod = Moderate	IV = Intravenous
ADL = Activities of Daily Living	Dec = Decreased

ESTIMATING SEVERITY GRADE

For abnormalities NOT found elsewhere in the Toxicity Tables use the scale below to estimate grade of severity:

- GRADE 1** **Mild** Transient or mild discomfort (< 48 hours); no medical intervention/therapy required
- GRADE 2** **Moderate** Mild to moderate limitation in activity - some assistance may be needed; no or minimal medical intervention/therapy required
- GRADE 3** **Severe** Marked limitation in activity, some assistance usually required; medical intervention/therapy required, hospitalizations possible
- GRADE 4** **Life-threatening** Extreme limitation in activity, significant assistance required; significant medical intervention/therapy required, hospitalization or hospice care probable

SERIOUS OR LIFE-THREATENING AEs

ANY clinical event deemed by the clinician to be serious or life-threatening should be considered a grade 4 event. Clinical events considered to be serious or life-threatening include, but are not limited to: seizures, coma, tetany, diabetic ketoacidosis, disseminated intravascular coagulation, diffuse petechiae, paralysis, acute psychosis, severe depression.

COMMENTS REGARDING THE USE OF THESE TABLES

- Standardized and commonly used toxicity tables (Division of AIDS, NCI's Common Toxicity Criteria (CTC), and World Health Organization [WHO]) have been adapted for use by the Division of Microbiology and Infectious Diseases (DMID) and modified to better meet the needs of participants in DMID trials.
- For parameters not included in the following Toxicity Tables, sites should refer to the "Guide For Estimating Severity Grade" located above.
- Criteria are generally grouped by body system.
- Some protocols may have additional protocol-specific grading criteria, which will supersede the use of these tables for specified criteria.

HEMATOLOGY				
	Grade 1	Grade 2	Grade 3	Grade 4
Hemoglobin	9.5 - 10.5 gm/dL	8.0 - 9.4gm/dL	6.5 - 7.9 gm/dL	< 6.5 gm/dL
Absolute Neutrophil Count	1,000-1,500/ mm ³	750-999/ mm ³	500-749/ mm ³	<500/ mm ³
Platelets	75,000-99,999/ mm ³	50,000-74,999/ mm ³	20,000-49,999/ mm ³	<20,000/ mm ³

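### Section 9.7 misstates the AST/ALT bands at two boundaries: exactly 3.0 x ULN is grade 2 (dosing may continue) there but grade 3 in Attachment 1 and a stop in 10.2, and exactly 2.0 x ULN has no grade

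*Protocol*

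**What the plan says.** Three parts of the Protocol set AST/ALT cut-offs.

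- **Section 9.7, AST and ALT Evaluation.** The lower bands are "Grade 1 (1.1 to <2.0 x upper limit of normal [ULN]), or Grade 2 (>2.0 to ≤3.0 x ULN"), and subjects in them may go on taking study drug. The upper bands are "Grade 3 (>3.0 to 8.0 x ULN), or Grade 4 (>8.0 x ULN"), and dosing then ends permanently. The scheme applies to confirmed abnormalities.
- **Attachment 1, Enzymes.** For both AST and ALT, grade 1 is 1.1 to <2.0, grade 2 is 2.0 to <3.0, grade 3 is 3.0 to 8.0 and grade 4 is >8 x ULN.
- **Section 10.2.** Study treatment must be discontinued for "AST or ALT increases ≥ 3 x ULN at screening, confirmed in a repeat test, to be performed within 48 hours" of the result reaching the site. The next item in 10.2 applies the same 48-hour repeat to other grade 3 or 4 screening abnormalities, with lipid exceptions.

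On which table governs, section 11.8 states: "The laboratory abnormalities will be determined according to the criteria specified in the DMID adult toxicity tables". The Adverse Events part of 9.7 uses the same tables for adverse events: "Grading will be determined according to the criteria specified in the DMID adult toxicity tables". Attachment 1 also carries a general comment: "Some protocols may have additional protocol-specific grading criteria, which will supersede the use of these tables for specified criteria".

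On retesting, the Clinical Laboratory Tests part of 9.7 says that for a grade 3 or 4 abnormality "a confirmatory test must be performed preferably within 48 hours but no later than 72 hours after the results have become available". The AST/ALT part says that for grade 3 or 4 "subjects should have a confirmatory measurement, preferably within 48 hours after the laboratory results become available to the site".

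**The concern.** A liver stopping rule should draw one line. Here the management section puts the boundary value on the continue side, while the discontinuation section and the grading table put it on the stop side. Section 1.2.4 singles out hepatobiliary effects for special safety attention, and section 9.1.2 lets dosing begin before the screening laboratory results are back. The screening result can therefore arrive in a subject who is already on drug.

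Two things follow at exactly 3.0 x ULN. The value would be managed as grade 2 but tabulated as grade 3. In addition, the grade triggers the retest in 9.7. A site that grades by the 9.7 bands sees grade 2 and finds no instruction there to repeat the test, yet the 10.2 stop takes effect only once a repeat has confirmed the value.

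**Working it through.** No sample size, power or error-rate figure is involved. The check compares inequalities.

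**Inputs**

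- 9.7: G1 if 1.1 ≤ x < 2.0; G2 if 2.0 < x ≤ 3.0; G3 if 3.0 < x ≤ 8.0; G4 if x > 8.0. G1 and G2 may continue; G3 and G4 stop.
- Attachment 1: G1 if 1.1 ≤ x < 2.0; G2 if 2.0 ≤ x < 3.0; G3 if 3.0 ≤ x ≤ 8.0; G4 if x > 8.0.
- 10.2: stop if x ≥ 3 at screening and confirmed on repeat.

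Here x is the value as a multiple of ULN. All three rules were evaluated from 1.10 to 10.00 in steps of 0.01.

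| x (multiple of ULN) | 9.7 | Attachment 1 | 10.2, confirmed screening value |
|---|---|---|---|
| 1.99 | G1, may continue | G1 | no stop |
| **2.00** | **no grade** | **G2** | no stop |
| 2.01 | G2, may continue | G2 | no stop |
| 2.99 | G2, may continue | G2 | no stop |
| **3.00** | **G2, may continue** | **G3** | **must stop** |
| 3.01 | G3, stop | G3 | must stop |
| 8.00 | G3, stop | G3 | must stop |
| 8.01 | G4, stop | G4 | must stop |

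On the whole grid, 9.7 and Attachment 1 differ at 2.00 and 3.00 only.

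**Consequence at each point.** At 2.00 there is none for treatment, because the grades on either side both allow dosing to continue. At 3.00 both the grade and the handling change.

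**Where the 3.00 mismatch can act.** The Time and Events Schedule takes biochemistry at screening, Day 8 and Day 21, and on Day 28 only if a visit is needed. Dosing is on Days 1 to 7. Only three kinds of sample can therefore bear on a dosing decision: the screening sample, an unscheduled sample, and a Day 8 sample from a subject still finishing the seven doses (section 9.1.3 has dosing continue until seven have been taken). For the screening sample, 10.2 is explicit and mandatory. For the other two, 9.7 is the only section with a specific AST/ALT threshold.

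**Retest limits.** The outer limit is 72 h in the general rule of 9.7 and 48 h in 10.2, a difference of 72 − 48 = 24 h. A repeat done within 48 h meets both rules and also the 48-hour preference in the AST/ALT part of 9.7.

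**After the fix.** With the Attachment 1 bands in 9.7, every value from 1.1 x ULN upward has exactly one grade, and the grade 3 stop begins at 3.0 x ULN, the same threshold as in 10.2.

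**The case against.** The best defence has four parts.

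1. *Attachment 1 allows protocol-specific criteria to override it, and 9.7 is one.* This could excuse 9.7 differing from Attachment 1, since a management cut-off and a reporting grade need not coincide. It cannot reconcile 9.7 with 10.2, because both are protocol text, and it does not supply a grade at 2.0 x ULN. A deliberate override would hardly leave that hole, and the Protocol gives no reason for different bands.

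2. *9.7 is permissive and 10.2 is mandatory, so a site that stops at a confirmed screening value of 3.0 x ULN complies with both.* This stands. The AST/ALT part of 9.7 also opens by leaving management to the investigator's judgement. A reader might infer that 9.7 orders dosing to go on where 10.2 forbids it, but the text does not say that.

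3. *The 9.7 bands have little room to act.* This also stands. No AST/ALT sample is scheduled between screening and the end of planned dosing, so 9.7 is decisive only for an unscheduled or late sample.

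4. *The 72-hour and 48-hour retest limits do not conflict.* This is correct. A reader might infer a second contradiction from them, but the 72 hours is a general outer limit for any grade 3 or 4 result at any time, and the 48 hours is a stricter rule for screening results that trigger discontinuation. The stricter rule governs.

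The retest problem that remains concerns the trigger and not the deadline. It also depends on which bands the site uses: one that grades by Attachment 1, or reads 10.2 directly, would repeat the test.

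**Conclusion.** The concern holds as a misstatement of two band boundaries in the AST/ALT part of section 9.7. At exactly 3.0 x ULN the section assigns a continue grade where Attachment 1 assigns grade 3 and where 10.2 requires a stop for a confirmed screening value. A reader using the 9.7 bands would also not be prompted to do the confirming retest. At exactly 2.0 x ULN the section assigns no grade, with no effect on treatment.

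The practical impact is minor: two exact values are affected and only one of them changes handling. That one arises mainly in the screening sample, where 10.2 already binds, and otherwise in an unscheduled or late on-treatment sample. This rests on taking the printed inequalities literally and on the sampling schedule as written. The documents do not support reading it as a general failure of the liver stopping rule, because every value above 3.0 x ULN is handled consistently. Nothing here touches the antiviral analysis. A correction is still warranted, because the misstated line is a stopping threshold and the remedy is exact.

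**What to change.** In the AST/ALT part of section 9.7, replace the bands with those of Attachment 1: grade 1 = 1.1 to <2.0, grade 2 = 2.0 to <3.0, grade 3 = 3.0 to 8.0, grade 4 = >8.0 x ULN. Leave the actions as they are. Treatment then stops at a confirmed value of 3.0 x ULN or more, as in 10.2, such a value triggers the retest, and 2.0 x ULN is grade 2.

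As an optional tidy-up, add to the general laboratory rule in 9.7 that screening abnormalities covered by 10.2 are retested within 48 hours of the result being available at the site. This should cover all the analytes that 10.2 covers and not AST/ALT alone.

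The cost is wording in 9.7. Section 10.2 and Attachment 1 stay as they are, and no visit or scheduled sample is added. The one change in conduct is that a value of exactly 3.0 x ULN is now retested under 9.7 and, if confirmed, ends dosing whenever it occurs.

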Day	-1 to 1 ^{b,c}	1	2	3	4-7	8	9-13	14 (±1)	15-20	21 (±3)	28 (±3)
	Screening / Baseline On-site	Treatment On-site		On-site visit ^d		On-site visit ^d		On-site visit ^d		On-site visit ^d	Phone follow-up (/ On-site visit) ^{d,e}
Body temperature ^p			X	X	X	X		X		X	X ^o
Mid-turbinate nasal swab: RSV viral load, viral sequencing ^{q,r}		X	X	X	X	X	X	X		X	
RI-PRO ^s	X	X ^u				X					
RiiQ Symtom Scale ^s	X	bid ^t	bid	bid	bid	bid	bid	X	X	X	
Additional questions about health and functioning ^s	X	bid ^t	bid	bid	bid	bid	bid	X	X	X	
RiiQ Impact Scale ^s	X	X ^u	pm	pm	pm	pm	pm	pm	pm	pm	
EQ-5D-5L ^s	X	X ^u	pm	pm	pm	pm	pm	pm	pm	pm	
Medical resource utilization	X	X	X	X	X	X	X	X	X	X	X
Safety Assessments											
Vital signs ^v	X			X		X		X		X	X ^o
Physical examination ^w	X			X		X		X		X	X ^o
ECG (triplicate 12-lead) ^x	X			X ^y		X				X	X ^o
Clinical Laboratory Assessments											
Blood sampling for hematology and biochemistry ^{z,aa}	X					X				X	X ^o
Blood sampling for coagulation tests ^{aa}	X					X				X	
Urinalysis ^{aa,bb}	X					X				X	
Renal function testing ^{cc}	X					X				X	
Pharmacokinetics											
Blood sampling for pharmacokinetics of JNJ-53718678 ^{dd}				X		X					
Exploratory Biomarker											
Blood sampling for host RNA assessment	X					X				X	

Phase	Screening / Treatment		Treatment Phase				Follow-up ^a				
Day	-1 to 1 ^{b,c}	1	2	3	4-7	8	9-13	14 (±1)	15-20	21 (±3)	28 (±3)
	Screening / Baseline On-site	Treatment On-site		On-site visit ^d		On-site visit ^d		On-site visit ^d		On-site visit ^d	Phone follow-up (/ On-site visit) ^{d,e}
Continuous Subject Review											
Adverse events ^{ee}	X	X	X	X	X	X	X	X	X	X	X
Concomitant medication ^{ff}	X	X	X	X	X	X	X	X	X	X	X

- a. Subjects who prematurely discontinue study drug treatment for any reason (except withdrawal of consent) will be asked to continue with their remaining study visits and assessment schedule, or, at a minimum, to return to the site for a Withdrawal and a Safety Follow-up Visit. Subjects who withdraw consent during the treatment or follow-up phase will be offered an optional Safety Follow-up Visit. At the Withdrawal and Safety Follow-up Visits, the same assessments as on the Day 8 and Day 21 visits, respectively, will be performed.
- b. Screening/baseline assessments start after signing of the ICF and can continue the next calendar day if needed. All screening/baseline procedures should take place prior to the first study drug intake.

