- y. ECG is to be performed post-dose (if feasible, 4 hours after dosing; otherwise as late as possible prior to leaving the site).
- z. Biochemistry blood samples at Day 8 and Day 21 will be taken preferably under fasted conditions (fasted for at least 10 hours).
- aa. Safety and coagulation laboratory tests will be done for each subject. Samples for clinical laboratory assessments will be collected and analyzed at a central laboratory. Any values that indicate a potential safety concern will be assessed by the investigator and appropriate follow-up actions, including potential discontinuation from treatment, will be carried out. Leftover blood samples may be used for exploratory biomarker analyses.
- bb. Urinalysis will be performed by the central laboratory and includes dipstick analysis, and if needed microscopic examination.
- cc. Includes determination of serum creatinine and estimation of the Glomerular Filtration Rate (GFR) based on creatinine by the Cockcroft-Gault formula²⁵; determination of serum cystatine C and estimation of the GFR based on cystatine C²⁵; determination of urinary creatinine, albumin, *N*-acetyl- β -glucosaminidase, β_2 -microglobulin, urinary phosphorus, sodium, potassium, and calcium.
- dd. Blood samples for determination of plasma concentrations of JNJ-53718678 will be collected on Days 3 and 8 at a random time point during the visit. The following information need to be recorded on the requisition form and/or the study medication log: date and time of study drug intake, date and time of pharmacokinetic blood sampling, time of meal if any in the time window of 2 hours before and 2 hours after study drug intake on the day of pharmacokinetic sampling. Samples can be used for the determination of plasma concentrations of metabolites of JNJ-53718678, excipients (eg, hydroxypropyl- β -cyclodextrin), protein binding, or endogenous markers for enzymes or transporters involved in the metabolism and distribution of JNJ-53718678, at the discretion of the sponsor.
- ee. All AEs and SAEs will be collected continuously from signing of the ICF (including diagnostic ICF, if applicable) onwards until the last follow-up visit (end of study visit). Any clinically significant abnormalities persisting at the end of the study/early withdrawal will be followed by the investigator until resolution or until a clinically stable endpoint is reached.

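### The AST/ALT stop in section 9.7 has no scheduled on-drug chemistry to act on, and sections 9.7 and 10.2 differ on its threshold and repeat limit

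*Protocol*

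**What the plan says.** Section 9.7 (AST and ALT Evaluation) lets dosing continue at grades 1 and 2. For grade 3 or 4 it says: "Subjects will permanently discontinue the intake of study drug". The scheme applies to confirmed values and names no visit, although it opens by leaving management to the investigator's judgement.

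The Time and Events Schedule shows dosing on Day 1 to Day 7. Its row "Blood sampling for hematology and biochemistry" is marked at screening, Day 8, Day 21 and, only if a visit is needed, Day 28. Footnote z fits this: "Biochemistry blood samples at Day 8 and Day 21 will be taken preferably under fasted conditions". Footnote b places all screening procedures before the first dose. The Day 3 visit has an ECG and a pharmacokinetic blood draw; footnote dd says those samples "will be collected on Days 3 and 8 at a random time point during the visit".

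Section 10.2 has two specific laboratory stops. The AST/ALT item covers screening values of at least 3 x ULN, "confirmed in a repeat test, to be performed within 48 hours of the result being available at the site". The same list contains a stop tied to an on-drug measurement: "The subject has a confirmed QTcF interval >500 ms at the Day 3 visit".

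Section 9.7 gives two further repeat rules. Under Clinical Laboratory Tests, for any grade 3 or 4 value: "a confirmatory test must be performed preferably within 48 hours but no later than 72 hours after the results have become available". Under AST and ALT Evaluation: "subjects should have a confirmatory measurement, preferably within 48 hours after the laboratory results become available to the site".

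**The concern.** A stopping rule protects subjects only if the site learns that the threshold has been crossed while doses remain. Doses 2 to 7 are mostly taken at home. A liver-enzyme rise without symptoms would first appear in the Day 8 sample, when a subject dosed to schedule has nothing left to withhold.

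The protocol gives its own reasons to care. Section 1.2.4 singles out hepatobiliary effects for special attention and says liver function will be monitored. Section 1.2.5 counts the discontinuation criteria in 10.2 among the measures that limit risk. The adults treated so far were healthy, or healthy and inoculated, and this trial adds comorbid adults. The QTcF rule shows the pairing that the liver rule lacks: a Day 3 measurement and a Day 3 stop.

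For a screening value, a site also meets three different time limits for the repeat, and at exactly 3.0 x ULN two different instructions.

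**Working it through.** The plan states no figure on this point, so there is none to reproduce. The check sets the texts side by side and then counts days and doses.

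**1. Scheduled chemistry while drug is taken.** Dosing days: 1, 2, 3, 4, 5, 6, 7. Chemistry days: screening (pre-dose), 8, 21, conditionally 28. Days common to both after dose 1: none. One caveat: section 9.1.3 heads the treatment period as running to Day 8, and section 6 mentions meal times around dosing on Day 8. A subject whose doses have shifted could still be dosing then. The schedule itself has no Day 8 dose.

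**2. The three texts on AST/ALT.**

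| Text | Applies to | Threshold to stop | Limit for repeat |
|---|---|---|---|
| 10.2, AST/ALT item | Screening values | ≥3 x ULN | 48 h |
| 9.7, AST and ALT Evaluation | Any time | >3.0 x ULN | Preferably 48 h, no outer limit |
| 9.7, Clinical Laboratory Tests | Any grade 3 or 4 value | None given | Preferably 48 h, at most 72 h |

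Attachment 1 (DMID table) puts 3.0 x ULN in grade 3. Section 9.7 puts it in grade 2, where dosing continues.

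**3. Timing.** The protocol gives no laboratory turnaround, so assume T = 1 or 2 days per central result. With sample day S and wait W for the repeat, confirmation falls on Day S + T + W + T. On Day d, 8 − d doses are left before that day's dose and 7 − d after it (none from Day 8).

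| Sample | Event | T = 1 | T = 2 |
|---|---|---|---|
| Day 1 screening, W = 2 | Confirmed | Day 5 (3/2 left) | Day 7 (1/0) |
| Day 1 screening, W = 3 | Confirmed | Day 6 (2/1) | Day 8 (0) |
| Day 3, added | First result | Day 4 (4/3) | Day 5 (3/2) |
| Day 3, added, W = 2 | Confirmed | Day 7 (1/0) | Day 9 (0) |
| Day 3, added, W = 0 | Confirmed | Day 5 (3/2) | Day 7 (1/0) |
| Day 8, current | First result | Day 9 (0) | Day 10 (0) |

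Screening on the day before Day 1 would move the first two rows one day earlier.

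Two things follow. The difference between 48 and 72 hours costs one day of a seven-dose course. A Day 3 sample helps little if the stop waits for a repeat taken at the 48-hour limit; it helps if drug is held on the first result.

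**4. How many subjects.** Section 1.1 reports only grade 1 or 2 graded laboratory abnormalities in the four pooled adult studies. It also gives 9 treated subjects with epistaxis as 7.5%, so the treated denominator is 9/0.075 = 120. With 0 events in n, the one-sided 95% upper bound is 1 − 0.05^(1/n):

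- n = 120: 2.47%. Of 50 active subjects (2 x 25) that is 1.23; of 42 (two thirds of the 63 minimum), 1.04.
- n = 50 (inoculated adults in the challenge study only): 5.82%, or 2.91 of 50.

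These bounds cover any grade 3 or 4 laboratory value, not only AST/ALT.

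**The case against.** The strongest reply is that a seven-dose course with routine tests at screening, Day 8 and Day 21 delivers the monitoring that 1.2.4 promises, and that mid-course chemistry was never promised. The safety record is clean. Besides the adults, interim data on 37 treated hospitalised children showed treatment-emergent laboratory abnormalities of at most grade 2. The dog liver-enzyme rises came at 250 mg/kg/day, ten times the 25 mg/kg/day NOAEL. That the dog NOAEL exposure (29,800 to 32,300 ng.h/mL) is 0.96 to 1.04 times the human AUC at 500 mg (31,200) therefore says little about the liver. This stands, and it limits the size of the point.

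A reader might infer that 10.2 confines laboratory stops to screening and so contradicts 9.7. The text does not support that. Section 10.2 never calls its list exclusive, and Attachment 5 orders a permanent stop for grade 2 to 4 rash with no matching item in 10.2. The screening items serve the situation in 9.1.2, where dosing may begin before results arrive. In the second laboratory item, the words about screening may attach only to the lipid exception.

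A reader might also infer that the 9.7 stop can never act. That is too strong. It can act on screening results that arrive after dose 1 (9.1.2) and on unscheduled safety samples (9.1.1). Sections 9.7 and 10.2 also let the investigator stop for any safety reason. None of these, however, finds a rise that gives no symptoms.

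On the repeat, a test within 48 hours satisfies all three texts. That is true, but a repeat at 60 hours breaks 10.2 and complies with 9.7 for the same screening value.

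Finally, a Day 3 sample confirmed at the 48-hour limit reads out on Day 7 or Day 9. That objection is correct, and it is why the added sample needs a hold on the first result.

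**Conclusion.** The concern holds in a limited form. There are 0 scheduled chemistry samples between dose 1 and dose 7. On scheduled data the 9.7 stop therefore reaches late screening results but not a rise that develops on drug. Separately, 9.7 and 10.2 disagree at exactly 3.0 x ULN and carry three versions of the repeat limit.

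The expected number affected is small: 0 to 1.2 of 50 active subjects on the pooled adult data, or 0 to 2.9 on the challenge-study adults alone. A reader might take the special attention to the liver as a sign of predicted harm. The clinical data give no such signal, so the case rests on a rule without a matching measurement. The day counts depend on the assumed turnaround of 1 to 2 days. The point concerns safety conduct and does not touch the sample size or the efficacy analysis. It deserves correction as a cheap improvement with a modest gain.

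**What to change.** 1. **Schedule.** Add serum chemistry, including AST, ALT and bilirubin, to the existing Day 3 blood draw. Haematology is optional.
2. **Scope and threshold.** In the 10.2 AST/ALT item, make the stop apply at screening or during treatment. In 9.7, start grade 3 at ≥3.0 x ULN and end grade 2 below 3.0, as in 10.2 and the DMID table. Leave the other laboratory item in 10.2 as it is.
3. **Repeat and hold.** Use the 48-hour limit of 10.2 in both places in 9.7. Hold study drug from the first grade 3 or 4 AST/ALT result until the repeat is known; otherwise confirmation of a Day 3 value at that limit falls on Day 7 to Day 9.

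Cost: 63 to 75 extra chemistry panels, with no new visit or needle stick, and short wording changes in 9.7 and 10.2. Some repeats will not confirm. Those subjects would be held for W + T days: 1 to 2 days with a same-day repeat, 3 to 4 days at the 48-hour limit. If held doses are skipped, as section 7 does for a dose more than 12 hours late, those doses are lost. A few subjects may also stop early. If the Day 3 panel is declined, the threshold and the repeat limit should still be aligned.
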